3.2 Method of Assigning Subjects to Treatment

Two groups, Group 1 and Group 2, will receive SB623 and sham surgery, respectively, in a 3:1 randomization scheme. Group 1 will be further randomized in a 1:1:1 ratio to receive either 2.5 million, 5 million, or 10 million SB623 cells. Randomization will be performed via an interactive web/voice response system (IXRS). For subjects in the United States enrolled outside of Japan, the randomization will be stratified by Glasgow Outcome Scale-Extended (GOS-E) score (i.e., scores 3, 4, 5 or 6); for subjects in Japan, the randomization will not be stratified.

3.3 Blinding

This is a double-blind study. The blind will be maintained by strict role definition and procedures described below:

Unblinded personnel:

- Cell preparation staff
- Unblinded study coordinator
- Surgeon and Operating Room staff
- Designated unblinded sponsor & clinical research organization (CRO) personnel
- Data and Safety Monitoring Board (DSMB) members and the supporting statistician and programmer involved in regular review and generation of unblinded safety data

Blinded personnel:

- Assessment site staff
- Designated blinded sponsor & CRO personnel

In order to maintain the blind the following procedures will be implemented:

- 1) Unblinded cell preparation staff will prepare and perform quality check of the cell suspension for each subject. The identity of the treatment will be concealed by the preparation of study product that is identical in packaging, labeling, schedule of administration, administration, and appearance.
- 2) The neurosurgeon and Operating Room (OR) staff will perform the sham surgery procedure using a surgical script that mimics the cell administration procedure as closely as possible (e.g., sequence of steps and overall time taken in the OR).
- 3) Subjects, assessment site staff, persons performing the assessments, blinded sponsor staff, and blinded CRO staff will remain blind to the identity of the treatment from the time of randomization until database lock and unblinding, using the following methods:
 - a. Randomization data are kept strictly confidential until the time of unblinding, and will not be accessible by any of the blinded study personnel in the study, unless subject level emergency unblinding is required as noted in section 11.1 of the protocol, Emergency Unblinding Procedures.
 - b. MRIs will be analyzed by a central reader post-surgery and blinded reports will be sent back to the assessment site staff (excluding the assessment site efficacy assessor) without any accompanying images. Description of the craniotomy skull defect and needle tract from the stereotactic surgical procedure are unblinding by definition and will therefore be excluded

from the blinded head MRI reports. If an unscheduled head MRI is to be done, the same process shall be followed as for the scheduled head MRI scans to maintain blinding, unless a local read is necessary for clinical care per the assessment site investigator's discretion. These unblinding events (e.g., local head imaging reading) will be recorded and reported to the Sponsor.

c. To further safeguard maintenance of the blind, primary and secondary efficacy assessments are to be completed solely by the efficacy assessors at assessment sites, who will be segregated from other activities at the assessment site and not have access to any patient study safety information (e.g., adverse events, concomitant medications, head imaging reports, medical charts, etc.).

d. All sites will be required to document how they will maintain the blind through a Maintenance of the Blind Plan that will require approval and sign off by the Sponsor.

3.4 Determination of Sample Size

For a two-sample t-test to show superiority of SB623 over sham surgery control, assuming 80% power, alpha of 0.05, a two-tailed test, and 3:1 randomization, a sample size of 48 (36 subjects in the treatment group and 12 subjects in the control group) is required. This assumes that the mean change from baseline to Week 24 in the FM-Motor Scale score is 10.0 for the treatment group (pooling all SB623 doses) and 3.0 for the control group, with an assumed standard deviation of 7.25 in each group. Based on an 8% upward adjustment to compensate for dropout patients, a total of approximately 52 subjects will be required. Since the analysis of efficacy is to be based on the modified ITT population, subjects will continue to be enrolled in the study until there are a total of approximately 52 subjects in the mITT population. The vast majority of subjects will be from outside of Japan; however, a sufficient number of Japanese patients are to be enrolled in order to address Japanese regulatory requirements.

3.5 Changes to the Protocol-Specified Analyses

An As Treated Population was added to the analysis populations.

The protocol stated that a mixed model repeated measures (MMRM) analysis with terms for treatment, visit, the baseline Fugl-Meyer Motor Scale score, the GOS-E score at screening, and the treatment-by-visit interaction would be performed for the primary efficacy endpoint. The model has been revised to now include terms for the baseline Fugl-Meyer Motor Scale score-by-visit interaction and the GOS-E score at screening-by-visit interaction.

The protocol stated that the following secondary efficacy endpoints would be analyzed in a manner analogous to that for the primary efficacy endpoint: the change from baseline in the Disability Rating Scale (DRS) score at Week 24, the change from baseline in the Action Research Arm Test (ARAT) total score at Week 24, the change from baseline in Gait Velocity at Week 24, and the change from baseline at Week 24 in the two NeuroQOL subdomain T scores (Upper Extremity Function (Fine Motor ADL) and Lower Extremity Function (Mobility)). Thus, the protocol specified model did not include terms for the baseline value of the endpoint-by-visit interaction or the GOS-E score at screening-by-visit interaction. These terms were added to the model for each of these endpoints.

The protocol stated that the primary efficacy endpoint and each of the above mentioned secondary efficacy endpoints would be analyzed to examine dose response, and that similar statistical methodology to that used to evaluate the SB623 combined doses vs. the sham surgery control treatment would be used, except that dose would be used instead of treatment and dose would be a continuous variable with the control treatment assigned a value of 0. Instead the MMRM analysis will be performed using a model with terms for visit, the interaction between SB623 dose and an indicator variable for the Week 4 visit, the interaction between SB623 dose and an indicator variable for the Week 12 visit, the interaction between SB623 dose and an indicator variable for the Week 24 visit, the baseline value of the endpoint, the baseline value of the endpoint-by-visit interaction, the GOS-E score at screening, and the GOS-E score at screening-by-visit interaction. The control treatment will not be included in this analysis.

4.0 EFFICACY AND SAFETY ENDPOINTS

For the mITT Population (see Section 6.1), patients with a Motricity Index UE Scale score at Screening of 10-81 will be considered to have an upper extremity deficit. Patients with a LE Scale score at Screening of 10-78 will be considered to have a lower extremity deficit. For the Per Protocol Population (see Section 6.2), patients with a Motricity Index UE Scale score at Screening of 10-81, at least two scores less than 33 with one of these less than 25, and at least one score greater than 0, will be considered to have an upper extremity deficit. Patients with a LE Scale score at Screening of 10-78, at least two scores less than 33 with one of these less than 25, and at least one score greater than 0, will be considered to have a lower extremity deficit.

4.1 Primary Efficacy Endpoint

The primary efficacy endpoint is the change from baseline in the Fugl-Meyer Motor Scale (FMMS) score at Week 24 among all patients.

4.2 Secondary Efficacy Endpoints

The secondary efficacy endpoints are as follows:

- Change from baseline in Disability Rating Scale (DRS) score at Week 24 among all patients
- Change from baseline in Action Research Arm Test (ARAT) total score at Week 24 (the affected side will be analyzed) among upper extremity deficit patients
- Change from baseline in Gait Velocity (10 meter walk time in seconds) at Week 24 (the better of the two trials at the visit will be used for analysis) among lower extremity deficit patients
- Change from baseline at Week 24 in T scores of NeuroQOL sub-domains:
- Upper Extremity Function (Fine motor ADL) among upper extremity deficit patients
- Lower Extremity Function (Mobility) among lower extremity deficit patients
- Global Rating of Perceived Change scores at Week 24 (from baseline) among all patients: assessed by the subject (may be completed by caregiver) and by the clinician

The ARAT total score is the sum of the scores from 19 tests spread across 4 subscales: grasp, grip, pinch, and gross movement. Each test is scored on an ordinal 4-point scale with 0=non movement, 1=the movement task is partially performed, 2=the movement task is completed but takes abnormally long, and 3=the movement is performed normally. If the score on the first test in a subscale = 3, then the score for that subscale is the maximum possible score (i.e., 3*number of tests). For the Gross Movement subscale, if the score on the first test = 0, then the score for that subscale = 0. For all other subscales, if the score on the first test does not equal 3 and the score on the second test = 0, then the score for that subscale = 0.

Items for the Neuro QOL Fine Motor ADL and Mobility subdomains are scored on an ordinal 5-point scale with 1=unable to do, 2=with much difficulty, 3=with some difficulty, 4=with a little difficulty, and 5=without any difficulty. The subdomain scores are the sum of the scores for the given domain. The Fine Motor ADL and Mobility raw scores are transformed to T-scores using tables 2 and 3, respectively.

Table 2 Adult Upper Extremity Function - Fine Motor, ADL

| Upper Extremity Function – Fine Motor, ADL 8-item Short Form (Adult) | | | | | |
|---|---------|-----|-----------|---------|-----|
| Raw Score | T-Score | SE | Raw Score | T-Score | SE |
| 8 | 12.8 | 2.0 | 25 | 27.3 | 2.0 |
| 9 | 13.7 | 2.3 | 26 | 28.0 | 2.0 |
| 10 | 14.7 | 2.4 | 27 | 28.7 | 2.0 |
| 11 | 15.8 | 2.5 | 28 | 29.5 | 2.0 |
| 12 | 16.9 | 2.4 | 29 | 30.2 | 2.1 |
| 13 | 18.0 | 2.4 | 30 | 30.9 | 2.1 |
| 14 | 19.0 | 2.3 | 31 | 31.7 | 2.1 |
| 15 | 19.9 | 2.2 | 32 | 32.6 | 2.2 |
| 16 | 20.8 | 2.1 | 33 | 33.5 | 2.3 |
| 17 | 21.6 | 2.1 | 34 | 34.5 | 2.4 |
| 18 | 22.4 | 2.1 | 35 | 35.6 | 2.7 |
| 19 | 23.1 | 2.0 | 36 | 37.1 | 3.2 |
| 20 | 23.9 | 2.0 | 37 | 39.3 | 4.2 |
| 21 | 24.6 | 2.0 | 38 | 41.2 | 4.5 |
| 22 | 25.3 | 2.0 | 39 | 43.7 | 4.7 |
| 23 | 26.0 | 2.0 | 40 | 53.8 | 7.8 |
| 24 | 26.7 | 2.0 | | | |

Table 3 Adult Lower Extremity Function - Mobility

| Lower Extremity Function - Mobility 8-item Short Form (Adult) | | | | | |
|--|---------|-----|-----------|---------|-----|
| Raw Score | T-Score | SE | Raw Score | T-Score | SE |
| 8 | 16.5 | 3.0 | 25 | 35.2 | 2.1 |
| 9 | 19.2 | 2.8 | 26 | 36.0 | 2.1 |
| 10 | 21.1 | 2.6 | 27 | 36.7 | 2.1 |
| 11 | 22.6 | 2.4 | 28 | 37.5 | 2.1 |
| 12 | 23.9 | 2.3 | 29 | 38.3 | 2.1 |
| 13 | 25.1 | 2.3 | 30 | 39.1 | 2.2 |
| 14 | 26.2 | 2.2 | 31 | 39.9 | 2.2 |
| 15 | 27.2 | 2.2 | 32 | 40.8 | 2.3 |
| 16 | 28.1 | 2.1 | 33 | 41.7 | 2.4 |
| 17 | 29.0 | 2.1 | 34 | 42.8 | 2.5 |
| 18 | 29.9 | 2.1 | 35 | 43.9 | 2.6 |
| 19 | 30.7 | 2.1 | 36 | 45.2 | 2.9 |
| 20 | 31.5 | 2.1 | 37 | 46.7 | 3.1 |
| 21 | 32.2 | 2.1 | 38 | 48.6 | 3.3 |
| 22 | 33.0 | 2.1 | 39 | 51.2 | 3.8 |
| 23 | 33.7 | 2.0 | 40 | 58.6 | 6.4 |
| 24 | 34.5 | 2.1 | | | |

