5.2 Parameters

5.2.1 Efficacy Endpoints

For the mITT Population, patients with a Motricity Index UE Scale score at Screening of 10-81 will be considered to have an upper extremity deficit, and patients with a LE Scale score at Screening of 10-78 will be considered to have a lower extremity deficit. For the Per Protocol Population, patients with a Motricity Index UE Scale score at Screening of 10-81, at least two scores less than 33 with one of these less than 25, and at least one score greater than 0, will be considered to have an upper extremity deficit, and patients with a LE Scale score of 10-78, at least two scores less than 33 with one of these less than 25, and at least one score greater than 0, will be considered to have an upper extremity deficit, and patients with a LE Scale score of 10-78, at least two scores less than 33 with one of these less than 25, and at least one score greater than 0, will be considered to have a lower extremity deficit.

The primary efficacy endpoint is the change from baseline in the Fugl-Meyer Motor Scale (FMMS) score at Week 24 among all patients. The secondary efficacy endpoints are as follows:

- Change from baseline in Disability Rating Scale (DRS) score at Week 24 among all patients
- Change from baseline in Action Research Arm Test (ARAT) total score at Week 24 among upper extremity deficit patients
- Change from baseline in Gait Velocity at Week 24 among lower extremity deficit patients
- Change from baseline in T scores at Week 24 of NeuroQOL Domains:
 - o Upper Extremity Function (Fine motor ADL) among upper extremity deficit patients
 - o Lower Extremity Function (Mobility) among lower extremity deficit patients
- Global Rating of Perceived Change scores at Week 24 (from baseline) among all patients: assessed by the subject (may be completed by caregiver) and by the clinician

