5.2.3 Exploratory Endpoints

- Change from baseline in Fugl-Meyer Motor Scale (FMMS) score at Week 24 among patients with both upper and lower extremity deficits
- Change from baseline in Fugl-Meyer Motor upper-extremity subscale (UE-FM) score at Week 24 among upper extremity deficit patients
- Change from baseline in Fugl-Meyer Motor lower-extremity subscale (LE-FM) score at Week 24 among lower extremity deficit patients
- Improvement by ≥6 points at Week 24 from Baseline in UE-FM score among upper extremity deficit patients
- Improvement by ≥3 points at Week 24 from Baseline in LE-FM score among lower extremity deficit patients
- Improvement by ≥10 points at Week 24 from Baseline in Fugl-Meyer Motor Scale (FMMS) score among patients with both upper and lower extremity deficits
- Improvement by ≥6 points at Week 24 from Baseline in Action Research Arm Test (ARAT) score among upper extremity deficit patients
- Improvement of at least one functional level [e.g., from <0.4 m/s to 0.4-0.8 m/s or from 0.4 0.8 m/s to >0.8 m/s] at Week 24 from Baseline in Gait Velocity on standard 10 m walk among lower extremity deficit patients

Pre- and post-contrast standard T1 and T2 weighted, dual echo, and FLAIR-MRI among all patients

- Diffusion tensor imaging (DTI) with tractography among all patients
- Perfusion MRI among all patients
- Lower limb motion as measured by leg activity monitor among lower extremity deficit Patients (applicable for US and Japan only)
- Outcome analysis among all patients based on genotyping of polymorphisms at 3 specific loci:
 - HLA degree of donor/recipient mismatch
 - BDNFVal66Met mutation present (yes/no)
 - ApoE (*i.e.*, homo and heterozygosity for ApoE2, ApoE3, ApoE4 alleles)

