15.8.2.4 Gait Velocity

Gait Velocity on a standard 10 m walk will be calculated at Baseline and Weeks 4, 12, 24 (secondary), 36 and 48. The treatment group will be compared to the control group based on the mean change from baseline at each month.

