18.2.2.1 Primary Efficacy Endpoint Analysis

The primary analysis will be a comparison of the mean change from baseline in the Fugl-Meyer Motor Scale score of SB623 treated subjects (pooling all SB623 doses) to sham surgical controls at 24 weeks. A mixed model repeated measures (MMRM) analysis will be performed with terms for treatment, visit, the baseline Fugl-Meyer Motor Scale score, the GOS-E score at screening, and the treatment-by-visit interaction. The Restricted Maximum Likelihood Estimation procedure will be employed using an unstructured covariance matrix. Missing observations will not be imputed.

Protocol TBI-01 Version 5, May 17, 2018

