18.2.2.2 Secondary Efficacy Endpoint Analyses

Secondary analyses will evaluate a number of outcomes:

- A. Comparison of the mean change from baseline in the Disability Rating Scale (DRS) score of SB623 treated subjects (pooling all SB623 doses) to sham surgical controls at 24 weeks will be performed in a manner analogous to that for the primary efficacy endpoint.
- B. Comparison of the mean change from baseline in the Action Research Arm Test (ARAT) total score of SB623 treated subjects (pooling all SB623 doses) to sham surgical controls at 24 weeks will be performed in a manner analogous to that for the primary efficacy endpoint. This analysis will be based on upper extremity deficit patients only.
- C. Comparison of the mean change from baseline in Gait Velocity of SB623 treated subjects (pooling all SB623 doses) to sham surgical controls at 24 weeks will be performed in a manner analogous to that for the primary efficacy endpoint. This analysis will be based on lower extremity deficit patients only.
- D. Comparison of the mean change from baseline in the two NeuroQOL subdomain T scores of SB623 treated subjects (pooling all SB623 doses) to sham surgical controls at 24 weeks will be performed in a manner analogous to that for the primary efficacy endpoint. The two subdomains include:
 - a. Upper Extremity Function (Fine Motor ADL)
 - b. Lower Extremity Function (Mobility)

The analysis of the Upper Extremity Function domain will be based on upper extremity deficit patients only, and the analysis of the Lower Extremity Function domain will be based on lower extremity deficit patients only.

E. The proportion of SB623 treated subjects (pooling all SB623 doses) scoring either 7 (much better) or 6 (a little better, meaningful) on the Global Rating of Perceived Change by both Subject and Clinician will be compared to sham-surgery controls at 24 weeks (from Baseline) using a logistic regression model with treatment (SB623 vs. sham placebo), the baseline Fugl-Meyer Motor Scale score, and the GOS-E score at screening as terms in the model. The outcome variable of this analysis is a dichotomized variable based on of the Global Rating of Perceived Change score (≥6 vs. <6).

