20.3.2 Justification for use of Gait Velocity as a secondary endpoint

Gait is commonly affected in TBI^{1, 2, 4, 38} and Gait Velocity is a useful outcome measure of lower extremity function as walking speed predicts the level of disability^{39, 40} as improvements are correlated with better quality of life.⁴¹ Furthermore, Gait Velocity measures are objective and have well defined thresholds.

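### The SAP analyses the protocol's Gait Velocity endpoint as walk time in seconds without listing this as a change, and leaves the handling of walk tests coded 999 in the MMRM unspecified

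*SAP*

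**What the plan says.** Protocol 5.2.1 lists "Change from baseline in Gait Velocity at Week 24 among lower extremity deficit patients". Protocol 15.8.2.4 says how it is obtained: "Gait Velocity on a standard 10 m walk will be calculated at Baseline". Protocol 18.2.2.2 plans a "Comparison of the mean change from baseline in Gait Velocity of SB623 treated subjects" with sham, by the method used for the primary endpoint. Appendix A, 20.3.2 gives the reason for the choice: "Gait Velocity is a useful outcome measure of lower extremity function as walking speed predicts the level of disability". The only gait unit in the protocol is in the exploratory responder endpoint of 5.2.3: "Improvement of at least one functional level [e.g., from <0.4 m/s to 0.4-0.8 m/s".

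SAP Appendix A, 4.2 defines the secondary endpoint as "Change from baseline in Gait Velocity (10 meter walk time in seconds) at Week 24", taking the better of two trials. SAP 10.4 confirms this: it equates gait velocity with walk time and treats gait as the one endpoint on which lower values are better. SAP 10.2 analyses it with the primary-type MMRM. SAP 4.3, item 8 keeps m/s for the responder endpoint.

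SAP 3.5 names "the change from baseline in Gait Velocity at Week 24, and the change from baseline at Week 24" among the endpoints whose model terms or dose-response model changed. It does not mention the scale.

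The rule for code 999 is in SAP 10.4: after blinded review, a patient who was not mobile receives 300 s, and a test not done for other reasons is missing. Its opening words confine it to the analyses in that paragraph, namely the Wilcoxon test and the shift table around 300 s. SAP 5.3 has imputation rules for the FMMS only, and SAP 10.1 and 10.2 are silent on the code.

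**The concern.** Gait is the only lower-limb performance test among the secondary endpoints. Under one name the SAP uses two scales with opposite directions of benefit, and the scale chosen for the main gait analysis is not the one the protocol names and justifies. Because time is a non-linear function of speed, the mean change in seconds cannot be converted into the mean change in velocity afterwards. A reader who relies on SAP 3.5 for departures from the protocol would not learn of this.

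The 999 gap bears on patients who gain or lose the ability to walk. A programmer could set the code to missing, use 300 s, or leave 999 in as a number. Each choice gives the MMRM a different result or a different set of patients, and nothing in the plan decides between them.

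**Working it through.** The plan gives no sample size, power or effect for gait, so there is no gait figure to reproduce. The sizing of 48 rests on the FMMS and is not touched.

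**1. Conversion.** On a 10 m walk, time (s) = 10 / velocity (m/s). Hence 0.4 m/s = 25 s, 0.8 m/s = 12.5 s, and 300 s = 10/300 = 0.033 m/s.

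**2. Weighting.** Change in seconds for the same gain of 0.1 m/s, at illustrative starting speeds:

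| Start (m/s) | Time before (s) | Time after (s) | Change (s) |
|---|---|---|---|
| 0.1 | 100 | 50 | -50 |
| 0.2 | 50 | 33.3 | -16.7 |
| 0.4 | 25 | 20 | -5.0 |
| 0.8 | 12.5 | 11.1 | -1.4 |

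The first change is 50/1.389 = 36 times the last.

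**3. Can the sign differ?** Two constructed cases, without variability:

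- Half of each arm starts at 0.2 m/s and half at 1.0. Sham is unchanged. SB623 goes from 0.20 to 0.19 (50 to 52.63 s) and from 1.0 to 1.2 (10 to 8.33 s). The velocity difference is (-0.01 + 0.20)/2 = +0.095 m/s, which is better. The time difference is (2.632 - 1.667)/2 = +0.48 s, which is worse.
- Two patients go from 0.20 to 0.25 m/s (50 to 40 s) and from 1.0 to 0.8 m/s (10 to 12.5 s). Mean velocity change is (0.05 - 0.20)/2 = -0.075 m/s, which is worse. Mean time change is (-10 + 2.5)/2 = -3.75 s, which is better.

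In the first case the arms have equal baselines. With GOS-E balanced as well, adjustment leaves both differences as they are, so covariate adjustment does not cure this.

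**4. Code 999.** Take one patient who cannot walk at baseline and walks at 0.4 m/s (25 s) at Week 24. The contribution to the arm mean is that patient's change divided by n. Arm sizes of 12 and 36 are assumptions (the planned arms of 48); the number with a lower-extremity deficit is not given, and smaller arms make the figures larger.

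| Handling in the MMRM | Change | Contribution, n = 12 | Contribution, n = 36 |
|---|---|---|---|
| Missing | none | none | none |
| 300 s | 25 - 300 = -275 s | -22.9 s | -7.6 s |
| Literal 999 | 25 - 999 = -974 s | -81.2 s | -27.1 s |
| 300 s converted to m/s | 0.4 - 0.033 = +0.367 m/s | +0.031 m/s | +0.010 m/s |

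These are contributions to a raw mean, not model-adjusted effects. They equal the shift from adding the patient only if the other patients' mean change is zero.

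**5. Which reading of 999?** Protocol 18.2.2.1 says of the primary model that "Missing observations will not be imputed", and 18.2.2.2 carries that method to gait. This points to missing. It is only one reading: 999 is a recorded code, and SAP 10.1 does not repeat the sentence.

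**The case against.** A reader might infer that the metric was switched covertly. The documents do not support that. Walk time is stated in SAP 4.2, repeated in 10.4 and printed in the figure titles. The protocol attaches no unit to the secondary endpoint itself, and its section 18.2.2 leaves the analysis of endpoints to the SAP. What stands is narrower: the name, the calculation and the rationale all point to velocity, and SAP 3.5 records other changes for this endpoint but not this one.

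The sign reversals are constructed. Each needs slow and fast walkers to move in opposite directions; if every treated patient in the first case had improved, the scales would agree. The documents give no speed distribution, so neither the reversal nor the 36-fold ratio is a forecast. This is right, and the unequal weighting holds without any reversal.

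One might also infer that patients unable to walk at baseline are definitely excluded from the gait MMRM. The text does not go so far; it leaves the matter open.

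Safeguards exist: a rank test, the shift table, the m/s responder endpoint and Table 14.2.46 in m/s. They reduce the harm but do not close the gap. The rank test still uses changes in seconds and the responder endpoint is coarse. Table 14.2.46 has no stated method and is absent from the main SAP's own table list. It may be post hoc, though the documents do not say so.

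**Conclusion.** The concern stands in a limited form, minor to should-fix. The main gait analysis estimates mean change in seconds, which is not the mean change in velocity that the protocol names, and SAP 3.5 does not record the difference. The weighting towards slow walkers follows from the algebra alone. Disagreement in sign is a possibility that depends on opposite changes in slow and fast walkers.

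The handling of 999 in the MMRM is unspecified. If the code is missing, patients who cannot walk at baseline drop out of that model although the Wilcoxon test counts them. If 300 s or the literal code is used, one such patient can contribute tens of seconds to a small arm's mean. The number of such patients is not given, so the practical size is unknown.

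The primary endpoint and the sample size are unaffected, and no loss or gain of power is claimed.

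**What to change.** - Keep the seconds MMRM as specified. Beside it, derive velocity = 10/time and run the same MMRM in m/s as the endpoint the protocol names. Use this as the stated method for Table 14.2.46. Label it post hoc if it is added after the interim unblinding described in section 3.0 of the SAP addendum.
- Apply the existing blinded 999 review in the same way to every gait analysis, including the dose-response models: not mobile = 300 s (0.033 m/s), other reasons = missing. All gait analyses then follow one rule.
- Add a sensitivity analysis that excludes non-walkers or, in m/s, scores them 0. Report their number by arm and visit.
- Record the scale in SAP 3.5.

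The cost is SAP wording, a one-line derivation, one further MMRM and one sensitivity analysis, all from data already collected; no patients or visits are added. There are three downsides: one more gait result in a plan without multiplicity control (SAP 5.6), a cluster of values at the floor, and possibly lower power in m/s, by an amount the documents do not allow one to estimate. The 300 s value also has strong leverage in the seconds model, which is why the analysis without non-walkers is needed.
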